1) **Title:** A Phase 2 trial of Neurokinin-1 Receptor Antagonist for the Treatment of Itch in Epidermolysis Bullosa patients

2) **PI:** [name], PhD

3) **Funding:** Epidermolysis Bullosa Research Partnership (SPO # 117763)

4) **Fund sources for this project:**

Epidermolysis Bullosa Research Partnership (EBRP) – provided funding
Menlo Therapeutics, Inc. – provided study medication

5) **Specific aims:**

This study aims to determine the safety profile of Serlopiant (or VPD-737) in children (>13 y.o.) and adults with pruritus associated with epidermolysis bullosa (EB). This study also aims to determine the efficacy of Serlopiant (5 mg) compared with placebo on reducing EB itch as measured by patient self-reports using a numeric rating scale (NRS) for itch severity and the Stanford EB itch questionnaire. A secondary aim of this study is to determine whether Serlopiant when compared with placebo reduces EB wounds and promotes healing as determined by serial photographs.

It is our hope that Serlopiant will reduce itch in adolescents and adults with EB.

6) **General background:**

NK1 receptor antagonists (Aprepitant and Serlopiant) were originally tested in clinical trials as an antiemetic and a medication to treat overactive bladder. Since 2005, NK1 receptor antagonists have been evaluated in 13 completed Phase I studies and two Phase 2b studies (N=300 subjects). Serlopiant has been well tolerated in young men at a single dose of 400mg, and in the elderly at a dose of up to 20mg. Repeat dosing of up to 50 mg a day for 4 weeks was well tolerated in young adults and elderly males. There were no drug-related serious adverse events (SAE) in these Phase I studies.

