There is a trend towards greater reduction in itch severity as measured by daily self-reported NRS itch severity for serlopitant 5 mg as compared to placebo during the two month active trial period, though this was not statistically significant.

8) Experimental design and data analysis:

Inclusion criteria:

1. Males or females who are at least 13 years of age.
2. Willing and able to understand and sign informed assent/consent. Adolescents will need a parent or guardian willing and able to give consent.
3. Clinical diagnosis of epidermolysis bullosa (DEB, EBS, or JEB).
4. Subjects must have pruritus of at least 6 weeks duration
5. History of chronic pruritus
6. On the Stanford EB Itch survey, subject must have a Screening Visit (Visit 1) NRS pruritus score of at least 4 on either (1) average itch score in the past 24 hours or (2) bathing/dressing itch score in the past 24 hours.
7. Female subjects must be of non-childbearing potential (ie, post-menopausal for at least 1 year, had a hysterectomy, or had a tubal ligation) or, if of childbearing potential, must have a confirmed negative urine pregnancy test prior to study treatment and be willing to use effective contraception for the duration of the trial. Effective contraception is defined as follows: oral/implant/injectable/ transdermal contraceptives, intrauterine device, condom with spermicide, or diaphragm with spermicide. Abstinence or partner's vasectomy is acceptable if the female agrees to use effective contraception if she decides to discontinue abstinence or to have sexual intercourse with a non-vasectomized partner.
8. Judged to be in good health based upon the results of a physical examination, medical history, and safety laboratory tests.

Exclusion criteria:

1. Have any medical condition or disability that would interfere with the assessment of safety or efficacy in this trial or would compromise the ability of the subject to travel to Stanford or to undergo study procedures or to give informed consent.
2. Have a history of sensitivity to any components of the study material.
3. Are females of childbearing potential who are unwilling to use adequate contraception or who are breast feeding.
4. Have any chronic or acute medical condition that, in the opinion of the investigator, might interfere with the study results or place the subject at undue risk.
5. Have chronic renal disease, ie, serum creatinine greater than 2 times the upper limit of normal.

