6. Have chronic liver disease, ie, AST or ALT greater than 2 times the upper limit of normal. Subjects with hepatitis B and C who have normal liver function may be enrolled.
7. Have a current malignancy (such as Hodgkin's lymphoma, B or T cell lymphoma, or myeloma) or blood cell dyscrasia (eg, polycythemia or myelofibrosis) that would lead to systemic chronic pruritus.
8. Subjects with untreated hyperthyroidism.
9. Have pruritus of psychogenic etiology (delusions of parasitosis, obsessive compulsive disorder and major depression) or neuropathic etiology (due to shingles, spinal cord injury or with neurologic deficit).
10. Have pruritus due to urticaria, drug allergy, or infection (such as pityriasis rosea or tinea or active human immunodeficiency virus [HIV]). Note: Subjects with HIV who have undetectable viral load, CD 4 counts >200 cells/cc, and stable retroviral therapy may enroll.
11. Have taken investigational medications within 30 days prior to Screening.
12. Are unwilling to discontinue specific pruritus medications for at least two weeks prior to initiation of study and throughout the study period (all severe CYP34A inhibitors - this

- includes **miconazole**, **delavirdine**, conivaptan, Clarithromycin, telithromycin, nefazodone, itraconazole, ketoconazole, indinavir, lopinavir, nelfinavir, **ritonavir**, saquinavir).
13. Within in the past 12 months, have expressed suicidal ideation with some intent to act.
 14. Started or changed medications, creams, or emollients including over-the-counter (OTC) preparations or bath oil treatment for relief of pruritus within 3 months prior to Screening.
 15. Have any social or medical condition (e.g. alcoholism, drug dependency, psychotic state) that, in the investigator's opinion, might interfere with the subject's ability to comply with the requirements of the protocol.

Statistical basis for the number of subjects to be enrolled:

This 14 patient clinical trial is powered only to determine large differences in the placebo (N=7) vs. 5 mg (N=14) groups. In power calculations, we assumed a mean of 8 NRS for the placebo vs. 5 NRS for the active with a SD of 3, and p-value of 0.05 (one sided).

| Two-sample t test with equal variances | | | | | |
|--|-----|------------------------|-----------|-------------------------|----------------------|
| | Obs | Mean | Std. Err. | Std. Dev. | [95% Conf. Interval] |
| x | 14 | 5 | 0.8017837 | 3 | 3.267852 6.732148 |
| y | 7 | 8 | 1.133893 | 3 | 5.225463 10.77454 |

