| combined | 21 | 6 | 0.7121396 | 3.263434 | 4.514503 7.485497 |
| diff | -3 | 1.38873 | | -5.906646 | -0.0933544 |
| Diff= mean (x) – mean (y) | | | | t = -2.1602 | |
| Ho: diff = 0 | | | | Degrees of freedom = 19 | |
| Ha: diff < 0 | | Ha: diff != 0 | | Ha: diff > 0 | |
| Pr(T < t) = 0.0219 | | Pr(T > t) = 0.0437 | | Pr(T > t) = 0.9781 | |

Statistical plan for analyzing at least the primary hypothesis:

The sample size is powered to detect small differences in NRS score. Because itch is subjective and varies daily, subjects will be asked to keep an itch diary every day. For each subject, we will plot their average itch scores over time before and after drug intervention. For each dosage group, we will use linear regression methods with mix effects (GLM, SAS) to track the change in itch in each of the groups from baseline. This study will provide the effect size, standard deviation and range of itch scores in EB patients in order to properly power a larger phase 2 trial. This study can detect large differences in itch scores should Serlopitant decrease itch from severe to low-none at 1 and 2 months. At the 3 month follow up, we will measure the durability and length of response.

Matrix showing procedure plan for each study visit:

| Schedule of Events for Phase 2 Serlopitant | | | | | | | |
|--|------------------|-----------------|------------------------------|----------------|----------------|----------------|----------------|
| | Screening period | | Treatment period | | | Follow up | |
| | Phone call | Visit 1 | | Visit 2 | Visit 3 | Phone call | Early Term |
| | Screening call | Screening visit | Determination of Eligibility | Month 1 | Month 2/EOT | Month 3 | |
| Examination | Day -60 to -30 | Day -44* to -1 | Months 6 to 0 | Day 30 ±14 | Day 60 ±14 | Day 90 ±14 | |
| Informed consent/ Photographic consent | | X | | | | | |
| Demographics | | X | | | | | |
| Medical history | | X | Review | | | | |
| Prior ^a & current medications | X | X | | X | X | X | X |
| Abbreviated physical examination | | X | | | X | | X |
| Vital signs | | X | | X | X | | X |
| Urine pregnancy test (UPT) ^b | | X | Review results | X | X | | X |
| Inclusion/exclusion criteria | X | X | | | | | |
| Blood samples for clinical laboratory tests ^c | | X ^c | Review results | X ^c | X ^c | | X ^c |
| Randomization | | | X ^h | | | | |
| NRS ^d & Stanford EB survey | | X | | X | X | X ^e | X |
| Photograph the affected area ^f | | X | | X | X | | X |

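### The plan for the primary hypothesis never writes the 5 mg minus placebo contrast or names its time point; read literally, it yields only a change from baseline in each arm

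*Combined protocol and SAP*

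**What the plan says.** Under Specific aims, the comparison is between arms: "This study also aims to determine the efficacy of Serlopiant (5 mg) compared with placebo on reducing EB itch". The statistical basis for the number of subjects is also between arms. There, "we assumed a mean of 8 NRS for the placebo vs. 5 NRS for the active with a SD of 3", at one-sided 0.05, and the table shown is a "Two-sample t test with equal variances" whose null hypothesis is a zero difference between the arm means.

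The section headed as the plan for the primary hypothesis describes a daily diary and a before-and-after plot for each subject. Its one modelling sentence is introduced as something done for every dose arm: "we will use linear regression methods with mix effects (GLM, SAS) to track the change in itch in each of the groups from baseline". It adds that large differences could be detected "should Serlopitant decrease itch from severe to low-none at 1 and 2 months", and that "This study will provide the effect size, standard deviation and range of itch scores in EB patients" so that a larger trial can be powered. Placebo is not mentioned in this section.

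The preliminary-data section reports a trend "for serlopitant 5 mg as compared to placebo during the two month active trial period, though this was not statistically significant". It gives neither the source of those data nor the method.

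**The concern.** The aim and the sample size ask whether 5 mg differs from placebo. The section that should define the answer tracks each arm against its own baseline. It gives no treatment term, arm-by-time term, contrast or decision rule, and it leaves two candidate time points open.

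The sample-size t test does not fill the gap. It compares NRS levels at an unnamed time, while the analysis section describes change from baseline in a mixed model. With daily diary data and 14 or 21 subjects, several defensible analyses remain open and the result may depend on which is picked.

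Two things are at stake. A change within the active arm is not an estimate of drug effect; the randomised difference is. And a stated purpose of the trial is to supply an effect size and SD for a larger study, yet the text does not say that this effect size is the between-arm difference.

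**Working it through.** **1. The plan's own figure.** Inputs from the sample-size section: means 5 and 8, SD 3, n = 14 and 7. SE = 3 × √(1/14 + 1/7) = 1.3887. t = −3 / 1.3887 = −2.1602 on 19 df, one-sided p = 0.0219, two-sided p = 0.0437. All match the printed table, so the sizing basis is a between-arm comparison.

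**2. The passages side by side.**
- Specific aims: 5 mg against placebo.
- Sample size: difference of two arm means, null value zero.
- Primary-hypothesis plan: change from baseline in each group, no contrast, Months 1 and 2 both named.
- Preliminary data: a 5 mg versus placebo result, no method.

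No other section supplies the missing contrast.

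**3. What a within-arm change contains.** Let δ be the drug effect, π the placebo response and ρ the regression to the mean. The active arm's change is δ + π + ρ and the placebo arm's is π + ρ. Only their difference isolates δ. The documents give no figure for π.

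**4. Size of ρ, if baseline is the Visit 1 score.** Entry is selective: "subject must have a Screening Visit (Visit 1) NRS pruritus score of at least 4 on either" of two items. From the plan: SD 3, cut-off 4. Assumed: population mean 6, screening-to-outcome correlation r = 0.5, item correlation 0.7, normal scores, and the second item related to the outcome only through the first.
- Formula: ρ = (1 − r) × (mean screening score of those who enter − population mean).
- Entry on either item: the excess is about 0.75, so ρ = 0.5 × 0.75 ≈ 0.4. The range is 0.1 to 1.1 for means 4 to 8 and r 0.3 to 0.7, and 0.05 to 1.40 if the item correlation also runs from 0.5 to 0.9.
- Entry on the outcome item alone: a = (4 − 6)/3 = −0.667, φ(a)/(1 − Φ(a)) = 0.427, excess = 3 × 0.427 = 1.28, so ρ = 0.5 × 1.28 = 0.64 (0.2 to 1.7 over the same means and r).

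**5. Size of ρ, if baseline is a separate pre-treatment diary mean.** ρ = (r_b − r_o) × excess, where r_b and r_o are the correlations of the screening score with baseline and with outcome. Equal correlations give zero. With r_b of 0.6 to 0.7 and r_o of 0.5, ρ is 0.1 × 0.75 to 0.2 × 0.75, or about 0.07 to 0.15.

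**6. Power of the contrast once written.** Noncentral t, difference 3, SD 3, one-sided 0.05. Two allocations are shown because the text calls this a 14-patient trial while the stated arms of 7 and 14 add to 21.
- 14 versus 7: SE 1.389, df 19, power 0.669, 90% interval half-width 2.40.
- 7 versus 7: SE 1.604, df 12, power 0.547, half-width 2.86.
- One baseline-adjusted score per subject, by simulation, at baseline-outcome correlation 0 / 0.3 / 0.5 / 0.7 (assumed): 0.647 / 0.683 / 0.755 / 0.880 at 14 versus 7, and 0.515 / 0.547 / 0.616 / 0.757 at 7 versus 7.

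**The case against.** The strongest reply is that the between-arm intent is plain. The aim and the sizing test state it, the primary-hypothesis section speaks of detecting differences in NRS, and tracking change in each group is common shorthand for a group-by-time model. The preliminary-data section even reports a 5 mg versus placebo comparison on daily NRS over two months. All of this stands as evidence of intent. It does not fix a model, a time point or an estimate, and the preliminary result is reported without a method.

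Three stronger readings are tempting, and the documents support none of them.
- A reader might infer that efficacy will be claimed from within-arm improvement. No sentence says so.
- A reader might infer that the results will carry about 0.4 points of regression to the mean. That needs the Visit 1 score as baseline. The plan does not define baseline, and the schedule's note d starts the daily diary at the screening visit. The population mean and correlations behind the figure are also assumed.
- A reader might infer that the next trial will be too small because the active arm's own change will be used to size it. The plan does not say which effect size it will carry forward.

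**Conclusion.** The point holds as a gap in specification: the primary comparison and its time point are unwritten, and the modelling sentence followed literally cannot answer the aim. This rests on the text and not on any simulated figure. The design and the data support the right analysis, so this is a cheap improvement and not a defect of the trial.

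The numerical consequence is conditional. Placebo response would be mixed into any within-arm change by an amount the documents do not allow one to state. Regression to the mean ranges from near zero to about 0.4 NRS points at central assumptions, depending on which baseline is used. A both-arm, baseline-adjusted contrast removes both. It also raises power from 67% to about 75% (14 versus 7) or from 55% to about 62% (7 versus 7) if baseline and outcome correlate at 0.5. If they do not correlate, adjustment costs a little: about 65% and 52%.

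**What to change.** Keep the plan's mixed model, fit it once to both arms, and replace the modelling sentence with:

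> Weekly mean diary NRS from all randomised subjects will be analysed in one linear mixed model with arm, time, arm-by-time and baseline NRS (mean of the pre-treatment diary days; if none, the Visit 1 24-hour average itch item), with random intercept and slope or unstructured covariance, and small-sample degrees of freedom. The primary estimate is the 5 mg minus placebo difference at Month 2 (last on-treatment week), tested at one-sided 0.05 with a two-sided 90% confidence interval. Within-arm changes are descriptive. The effect size and SD carried to the larger trial are those of the between-arm difference.

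The primary week is defined as on treatment because the Month 2/EOT visit may fall anywhere from Day 46 to Day 74 (Day 60 ± 14), so a fixed study day could fall after the last dose for some subjects. The fallback names one item because the entry criterion lists two. The covariance structure should be settled before analysis: about eight weekly means make 8 × 9 / 2 = 36 unstructured parameters, many for 14 to 21 subjects.

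The cost is wording, since daily NRS is already collected. Downsides:
- Within-arm improvement no longer counts as evidence of efficacy.
- Power stays modest, as shown above. The adjusted figures are for a single score per subject, not for the mixed model itself.
- Subjects who stop early contribute the weeks they recorded, so the estimate relies on a missing-at-random assumption that should be stated.
- The pre-treatment diary may be short, and one reading of the schedule note sends it with the medication; hence the fallback.
- If the preliminary data come from this trial, which the text does not say, the amendment must state that the contrast was fixed after that look.

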| Dispense study medication | | | X ^h | X | | | |
| Dispense subject diary | | X | X ^h | X | X ^g | | |
| Review/collect diary with subject | | | | X | X | X | X |
| Review and record adverse events | | | | X | X | X | X |

Note: NRS = numeric rating score.

* Includes up to 30 day washout from prohibited medications. The study medication and diary dispensation are to occur no more than 1-2 weeks after Screening Visit.

- a: all medications taken within 30 days prior to screening.
- b: for females of child-bearing potential.
- c: all subjects: hematology, serum chemistry will be measured at Screening, Month 1, and Month 2/EOT or early termination (ET).
- d: NRS recorded by subject daily, using diary, from screening visit through the end of the study; NRS is included in the Stanford EB Itch survey.
- e: the Stanford EB survey will be administered over the phone by a member of the research staff.
- f: photographs taken only if patient has signed photography consent
- g: a return envelope will be provided for the patient to return the study diary to Stanford after the follow up phone call

| | Schedule of Events for Phase 2 Serlopitant | | | | | | |
|--|--|---------|------------------|---------|---------|------------|------------|
| | Screening period | | Treatment period | | | Follow up | |
| | Phone call | Visit 1 | | Visit 2 | Visit 3 | Phone call | Early Term |

h: Patient letter of enrollment and study medication will be mailed to patient after determination of eligibility following the Screening Visit

Each subject will be un-blinded individually after completing 3 months of study period. All patients who complete the study will be offered a 2-month trial on active drug. Patient who received active drug in the first phase will be contacted and asked if they would like to continue on active drug for an additional 2 months. Patients who received placebo in the first phase will be contacted and asked if they would like to repeat the study on open label for 2 months.

When this occurs, the schedule of events will be as follows:

Patients who would like to continue with the treatment for the open-label extension portion of the study will be provided with the research medication and research daily diary. They will be followed up by phone at baseline, 1 month, 2 months, and 3 months (wash out). In addition, they will go to an external lab near their home for lab monitoring that will occur once a month for the two months they are on active drug.

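### The only efficacy model is called mixed-effects but assigned to SAS GLM and describes change within each group; depending on how it is run, the inference could be wrong, and no between-arm contrast is stated

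*Combined protocol and SAP*

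**What the plan says.** Section 8 of the combined protocol and SAP, under the heading on the statistical plan for the primary hypothesis, has a single modelling sentence. For each dosage group it proposes "linear regression methods with mix effects (GLM, SAS) to track the change in itch in each of the groups from baseline". The same paragraph explains that, because itch varies from day to day, "subjects will be asked to keep an itch diary every day", and that for each subject "we will plot their average itch scores over time before and after drug intervention". Footnote d to the Schedule of Events confirms the frequency and span: "NRS recorded by subject daily, using diary, from screening visit through the end of the study".

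The sample-size section sets out the arms as "This 14 patient clinical trial is powered only to determine large differences in the placebo (N=7) vs. 5 mg (N=14) groups" (the sentence gives 14 patients in total, while its arm sizes sum to 21). It uses a two-sample t test with one value per patient: "Degrees of freedom = 19".

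The plan does not state the random effects or covariance structure, the degrees-of-freedom method, whether daily scores or averages enter the model, how missed diary days are handled, or which between-arm difference is tested and when. Section 5 (Specific aims) asks for the efficacy of serlopitant 5 mg against placebo.

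**The concern.** There are two problems in one sentence.

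**The tool and the method do not match.** A mixed model for repeated scores lets each subject have a level, and possibly a slope, of their own, and tests treatment against variation between subjects. SAS GLM is a least-squares procedure for fixed effects. By default it tests against residual error, so 60 days from one patient count almost as 60 patients. In its repeated-measures layout, with one column per day, it keeps only subjects with every day present. With 60 columns and 19 error degrees of freedom (12 if the trial has 14 patients), its multivariate tests cannot be formed.

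**The estimand does not match the aim.** Tracking change from baseline inside each group is not a comparison with placebo. One arm can improve clearly and the other less clearly without any demonstrated difference between them.

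This is the only inferential efficacy method in the document, and the same paragraph says that the results will supply the effect size and SD for a larger trial. A false positive, or an SD that mixes within-patient and between-patient variation, would carry forward into that design.

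**Working it through.** **1. The plan's own figure.** Inputs from the sample-size section: 14 and 7 patients, "we assumed a mean of 8 NRS for the placebo vs. 5 NRS for the active", and "SD of 3, and p-value of 0.05 (one sided".

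- SE = 3 × √(1/14 + 1/7) = 1.3887
- t = (5 − 8)/1.3887 = −2.1602, with 14 + 7 − 2 = 19 degrees of freedom
- one-sided p = 0.0219, two-sided p = 0.0437

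All of these match the printed table. The planning calculation therefore treats the patient as the unit. No figure is stated for the mixed-model analysis.

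**2. Daily rows treated as independent: hand calculation.** The documents give no split of variance within and between patients, so the following is assumed: between-subject SD 2, daily SD 1.5, 60 treatment days (Month 2 is Day 60).

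- Intraclass correlation = 2²/(2² + 1.5²) = 4/6.25 = 0.64
- Design effect = 1 + (60 − 1) × 0.64 = 38.8, so the standard error is too small by √38.8 = 6.2
- One-sided 5% test: 1 − Φ(1.645/6.23) = 1 − Φ(0.264) = 0.40

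**3. Simulation under no treatment effect.** Same variances, lag-1 correlation 0.5, subject-slope SD 0 to 2 points over 60 days, 14 v 7 and 7 v 7, 2,000 trials per setting, nominal one-sided 5%.

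| Analysis | False-positive rate |
|---|---|
| Group, daily rows, residual error | about 40% (39% to 42%) |
| Group-by-day, subject as a factor, residual error, slope SD 0 | 15% to 18% |
| same, slope SD 1 | 22% to 24% |
| same, slope SD 2 | 29% to 32% |
| Comparison of subject-level slopes | about 5% |

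**4. Sensitivity to the assumed correlation.** Total SD set to the plan's 3, 7 v 14, 60 days, two-sided 5%. The error rate is 2 × [1 − Φ(1.96/√DE)], where DE = 1 + 59 × ICC.

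| ICC | DE | SE too small by | Formula | Simulated |
|---|---|---|---|---|
| 0.2 | 12.8 | 3.6 | 0.58 | 0.58 |
| 0.5 | 30.5 | 5.5 | 0.72 | 0.73 |
| 0.8 | 48.2 | 6.9 | 0.78 | 0.78 |

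With the subject as the error term, the simulated error for group was 0.037 to 0.061, including 0.046 with 10% of days missing at random. Group-by-day against residual error was sound (0.047 to 0.058) when subjects differed only in level. It rose to 0.25 with lag-1 correlation 0.5, and to 0.28 with a subject-slope SD of 1.5 points.

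**5. One column per day.** If a fraction m of days is missed independently (assumed), the chance of a complete 60-day record is (1 − m)^60.

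| m | Complete | Of 21 | Of 14 |
|---|---|---|---|
| 1% | 0.99^60 = 0.547 | 11.5 | 7.7 |
| 2% | 0.98^60 = 0.298 | 6.2 | 4.2 |
| 5% | 0.95^60 = 0.046 | 1.0 | 0.6 |

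**The case against.** A reader might infer that the planned p-values and intervals are bound to be wrong. The documents do not support that, for four reasons that stand:

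- The stated method is mixed effects, and the plan does not write PROC GLM. The abbreviation may be loose shorthand for a general or generalized linear mixed model.
- Even PROC GLM can test group against a subject error term (RANDOM with its TEST option, or a TEST statement). That keeps incomplete subjects and gave close to 5% in step 4.
- The plan does not say that daily rows enter the model. It mentions averages for plotting and differences at 1 and 2 months. With averages, the 60-column figures do not apply.
- Dropping incomplete subjects costs precision, and can bias results if diaries are not missing completely at random. It does not by itself invalidate a p-value.

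It is also fair that every variance component and miss rate above is assumed, and that the group and group-by-day tests in the simulation are not stated in the plan.

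These points limit the claim without removing it. The subject-error-term route protects the group test, but GLM's standard errors for estimates do not generally adjust, and its tests of time trend still fail under day-to-day correlation or differing slopes. Change over time is what the sentence sets out to follow. If the abbreviation was only shorthand, the model still has no stated structure and no between-arm contrast.

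**Conclusion.** The point holds as a conflict between method and tool, together with a missing between-arm contrast. The inference could be wrong, depending on an implementation that the plan leaves open.

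The direction of the error under naive use on daily rows does not depend on the assumptions, provided that scores are positively correlated within a patient. The size does. It is about 40% for group and 15% to 32% for group-by-day at a nominal one-sided 5%, with between-subject SD 2, daily SD 1.5 and lag-1 correlation 0.5. For group, it is 58% to 78% at a nominal two-sided 5% for ICC 0.2 to 0.8. The loss of subjects in the one-column-per-day layout rests on assumed, independent missed days.

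That the sentence describes change within groups while the aim is a comparison with placebo can be read from the text and needs no assumption.

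**What to change.** Replace the bracketed tool and the within-group wording with one model:

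- **Procedure:** PROC MIXED or GLIMMIX, fitted to both arms together.
- **Response:** daily or weekly-mean NRS (state which), using all available diary data, with no deletion of subjects for missed days.
- **Fixed effects:** treatment, time, treatment-by-time and baseline NRS.
- **Within-subject structure:** a subject-level random effect or a within-subject covariance, for example random intercept and slope with first-order autoregressive errors, and a small-sample degrees-of-freedom method such as Kenward-Roger.
- **Fallback:** a simpler covariance, named in advance, in case a random slope plus autoregressive errors does not converge with 14 to 21 subjects.
- **Main contrast:** the between-arm difference at Month 2.
- **Check:** a baseline-adjusted comparison of each subject's 7-day mean at Month 2.

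The cost is a few sentences of specification and no new data. Intervals will be wider than those from a naive GLM, because they will reflect the number of patients and not the number of diary days.

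### The primary analysis tracks change from an undefined baseline within each arm; one baseline-adjusted model comparing the arms would serve the stated aim better

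*Combined protocol and SAP*

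**What the plan says.** Section 5 sets the aim: efficacy of 5 mg against placebo on self-reported itch, by NRS and by the Stanford EB itch questionnaire.

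The statistical plan in section 8 has two sentences on how baseline enters. The first is descriptive: "For each subject, we will plot their average itch scores over time before and after drug intervention". The second is the model, a mixed-effects linear regression described by dose group, "to track the change in itch in each of the groups from baseline". Neither says which pre-dose scores form the baseline, whether baseline is a covariate, or what contrast compares the arms.

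The sample-size paragraph is a two-arm calculation on NRS levels: "we assumed a mean of 8 NRS for the placebo vs. 5 NRS for the active with a SD of 3", with 7 on placebo and 14 on 5 mg.

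Pre-dose data are planned. Footnote d of the Schedule of Events reads "NRS recorded by subject daily, using diary, from screening visit through the end of the study". The row "Dispense subject diary" is marked at Visit 1 and again, with footnote h, at the determination of eligibility. Footnote * says "The study medication and diary dispensation are to occur no more than 1-2 weeks after Screening Visit". Footnote h says "study medication will be mailed to patient after determination of eligibility following the Screening Visit". The row "NRS ^d & Stanford EB survey" has one pre-treatment mark, at Visit 1, and inclusion criterion 6 takes its threshold of 4 from that same survey.

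**The concern.** A change within each arm does not estimate the effect of 5 mg relative to placebo. It mixes drug effect with placebo response, natural fluctuation and selection at entry. If the two within-arm results are then set side by side, the larger active arm (14 against 7) is more likely to reach significance even when both arms improve equally.

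Baseline is also left open. The Visit 1 survey score, the last diary day, and a mean over some set of diary days all fit the text. The plan itself notes that itch varies from day to day, so these choices can give different answers.

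Finally, the arms are small enough for chance imbalance at baseline to be common. A covariate built from diary days already planned would account for it at almost no cost.

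**Working it through.** **1. The plan's own figure.** Inputs from section 8: means 5 and 8, SD 3, n = 14 and 7.

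- SE = 3 × √(1/14 + 1/7) = 1.3887
- t = −3 / 1.3887 = −2.160, with 14 + 7 − 2 = 19 df
- one-sided p = 0.0219, two-sided p = 0.0437

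This matches the printed output. It compares levels between arms and uses no baseline. I take 7 + 14 = 21 subjects throughout; the 14-patient total in the same paragraph is a separate inconsistency.

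**2. Chance imbalance.** If baseline SD is also 3 (assumed), the SE of the baseline difference is 1.39. An imbalance of 1 point or more then has probability 2 × (1 − Φ(1/1.39)), about 47%.

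**3. What side-by-side within-arm tests would do.** Assume both arms truly fall by the same amount and each is tested by a one-sided 5% one-sample t test. The SD of change is 3 × √(2(1 − ρ)), which is 3.00 at ρ = 0.5 and 2.32 at ρ = 0.7. The chance that active is significant and placebo is not is P(active) × (1 − P(placebo)):

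| Common fall | ρ | Active | Placebo | Active only |
|---|---|---|---|---|
| 1 | 0.5 | 0.322 | 0.195 | 0.26 |
| 1 | 0.7 | 0.453 | 0.263 | 0.33 |
| 2 | 0.5 | 0.763 | 0.467 | 0.41 |
| 2 | 0.7 | 0.919 | 0.643 | 0.33 |

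**4. Covariate against simple change.** The documents give no correlation or day-to-day variance, so these are assumed. Total variance is 9 = Vb + Vw, with Vb 80% or 50% of it. The true-level correlation r from baseline to Month 2 is 0.5 or 0.7. Days are independent, and baseline and outcome are both 7-day means, so W = Vw/7.

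- Variance of simple change = 2(Vb + W) − 2rVb
- Residual variance with covariate = Vb + W − (rVb)²/(Vb + W)

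Example, Vb = 7.2, r = 0.5: W = 1.8/7 = 0.257. Change: 14.914 − 7.2 = 7.71. Covariate: 7.457 − 12.96/7.457 = 5.72.

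The average 95% CI half-width was then simulated for 7 versus 14, with 19 df for change and 18 for the covariate model. The first version uses unbounded normal scores. The second rounds and clips daily scores to 0-10, requires an entry score of at least 4 and sets the pre-selection mean at 8, the plan's placebo mean.

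| Vb share, r | Variance: change → covariate | Half-width, unbounded | Half-width, 0-10, mean 8 |
|---|---|---|---|
| 0.8, 0.5 | 7.71 → 5.72 | 2.65 → 2.36 (11%) | 2.19 → 2.10 (4%) |
| 0.8, 0.7 | 4.83 → 4.05 | 2.11 → 1.99 (6%) | 1.80 → 1.81 (none) |
| 0.5, 0.5 | 5.79 → 4.16 | 2.30 → 2.01 (13%) | 1.89 → 1.77 (7%) |
| 0.5, 0.7 | 3.99 → 3.21 | 1.91 → 1.77 (7%) | 1.61 → 1.57 (2%) |

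At a bounded mean of 6 the gain is 3-11%. Power for a 3-point difference at one-sided 5% goes from 73% to 81% in the first row and from 93% to 96% in the last row when unbounded. On the bounded scale at mean 8 (the 3 points applied before clipping), those rows go from 76% to 79% and from 94% to 95%.

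**5. When adjustment would lose.** Let c be the correlation between the baseline and Month 2 7-day means. With 21 subjects, estimating the slope costs a factor of 18/17 on average.

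- Against change: (1 − c²)(18/17) < 2(1 − c) gives 1 + c < 34/18, so c < 0.889
- Against no adjustment: (1 − c²)(18/17) < 1 gives c² > 1/18, so c > 0.236

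The four cells have c = rVb/(Vb + W) = 0.48, 0.68, 0.44 and 0.61, all inside this range. These limits are for the unbounded scale; bounding removes the gain in one cell, as the table shows.

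**The case against.** The strongest objection is that simple change is not clearly the plan's analysis. The plan names a mixed model on daily scores, and its text is too short to exclude one that takes the pre-dose days as outcomes. That stands: the gains above cannot be charged to the plan as written. It has a limit, though. Such a model recovers the benefit of adjustment if it holds the arms to a common pre-dose mean. With a separate pre-dose mean per arm and complete data, its arm-by-time contrast reduces to simple change.

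A second objection is that this is a pilot meant to supply an effect size and SD for a larger trial. This lowers the urgency, but those estimates also depend on how baseline and the contrast are defined.

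Three stronger readings are tempting and are not supported:

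- **That no comparison with placebo is intended.** The aim and the two-sample calculation both point to one, and section 7 reports its trend for 5 mg against placebo. The contrast is unwritten, not ruled out.
- **That pre-dose diary data may not exist.** Footnote d and the Visit 1 mark both start the diary at screening. Footnote * fits the second issue, which goes out with the medication. Its wording is loose, no more.
- **That the entry threshold biases the result.** Regression to the mean affects both arms alike, so the between-arm contrast is unbiased on average. In simulations of entry at 4 or more with no drug effect, the within-arm fall from Visit 1 was 0.06-0.30 points at mean 8 and up to 1.11 at mean 5. It matters only if that fall is read as drug effect.

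**Conclusion.** The point holds in a limited form. The plan's aim is a comparison with placebo, but its primary analysis is worded as within-group change from a baseline it does not define, with no covariate and no stated contrast. A single baseline-adjusted comparison of the arms is a better-specified method and almost free.

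The firmer reason for it is interpretive: within-arm changes set side by side could favour the larger arm in 26-41% of trials with equal falls of 1-2 points. That applies only if the results are read that way, which the plan does not say. The precision argument is weaker. It depends on assumed variance shares and correlations, shrinks to 0-7% at mean 8 once the scale is bounded, and may vanish against a well-specified mixed model. I would put this to the sponsor as a change worth considering, not as a required correction.

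**What to change.** - **Model.** Fit one mixed model across both arms with arm, time, arm-by-time and baseline NRS. Define baseline as the mean of the last 7 available diary days before first dose. To much the same effect, enter the pre-dose days as outcomes in one model with an arm-by-time term and a common pre-dose mean for both arms.
- **Conclusion.** Base it on the between-arm contrast at Months 1 and 2, not on within-arm change.
- **Visit 1 scores.** Use the Visit 1 NRS for eligibility only. Compare the arms on the Stanford survey adjusting for its Visit 1 score.
- **Minor wording.** Let footnote * refer to the second diary issue. State where the first-dose date is recorded, since the baseline window ends there and the drug is mailed. Reconcile the screening and washout timing passages: the Day −44 window, the washout of up to 30 days, the two weeks in exclusion criterion 12, the 1-2 weeks in footnote *, and the months shown for the eligibility column. They do not say whether washout comes before or after Visit 1.

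**Cost.** Analysis text and small schedule edits, with no added visit. The covariate takes one degree of freedom (19 to 18), and subjects with few pre-dose days will have a noisier baseline. Section 7 reports daily NRS results without naming their source. If they come from this trial, the definition can no longer be fixed before data are seen, and the report should say so.
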